12.5.3. Reporting Standards for Pharmacokinetic

Pharmacokinetic Concentration Data	
Descriptive Summary Statistics, Graphical Displays and Listings	
 Refer to IDSL PK Display Standards. Refer to IDSL Statistical Principle 6.06.1. Note: Concentration values will be imputed as per GUI_51487 for descriptive summary statistics/analysis and summarized graphical displays only.
NONMEM/PK/PD File	
 PK/PD file (CSV format) for the PK/PD analysis by Clinical Pharmacology Modelling and Simulation function may be created according to the data specification detailed in Appendix 12: NONMEM datafile Specification.

12.6. Appendix 6: Derived and Transformed Data

12.6.1. General

Multiple Measurements at One Analysis Time Point

 • Mean of the measurements will be calculated and used in any derivation of summary statistics but if listed, all data will be presented. • Participants having both High and Low values for Normal Ranges at any post-baseline visit for safety parameters will be counted in both the High and Low categories of “Any visit post-baseline” row of related summary tables. This will also be applicable to relevant Potential Clinical Importance (PCI) summary tables.
Study Day

 • Calculated as the number of days from First Dose Date: 
 • Ref Date = Missing → Study Day = Missing • Ref Date < First Dose Date → Study Day = Ref Date – First Dose Date • Ref Date ≥ First Dose Date → Study Day = Ref Date – (First Dose Date) + 1

12.6.2. Study Population

Demographics
Date of Birth

 • Only the year of birth will be captured, and therefore the date of birth is then derived as follows: Year of birth = YYYY → Date of birth = 30th June YYYY
Age

 • Calculated as the integer part of (date of screening – date of birth) Age = integer part (date of study day 1 – 30th June YYYY) • Birth date will be presented in listings as ‘YYYY’.
Body Mass Index (BMI)

 • Calculated as Weight (kg) / [Height (m)²]
Race category

 • White: ‘White: Arabic/North African Heritage’ and ‘White: White/Caucasian/European Heritage’, or both of these, but no other category checked. • African descent: ‘African American/African Heritage’, and no other category checked. • Asian: ‘Asian – Central/South Asian Heritage’, ‘Asian – East Asian Heritage’, ‘Asian – Japanese Heritage’, and ‘Asian – South East Asian Heritage’, or any combination of these, but no other category checked. • Other: Any combination that has not been categorized above (‘mixed race’).
Treatment Compliance

 • Participant compliance will be based on the number of expected tablets to be taken and the number actually taken and will depend on whether a participant was taking investigational product (two tablets) twice a day or three times a day. • Treatment compliance will be calculated based on the formula: 
 • Treatment Compliance = (Total tablets taken/total tablets expected to be taken) *100 • Total tablets taken = (Total number of Tablets Dispensed-Total Tablets Returned) • Total Tablets expected to be taken is duration of exposure*4 (see derivation below) for BID participants and *6 for TID participants.

Demographics

 Note compliance will only be calculated for participants who took at least one dose (i.e. number of tablets taken is >=1).
Extent of Exposure

 Number of days of exposure to study drug will be calculated based on the formula: 
 Duration of Exposure in Days = Treatment Stop Date – (Treatment Start Date) + 1 Participants who were randomized but did not report a treatment start date will be categorised as having zero days of exposure. 
 The cumulative dose will be based on the formula: Cumulative Dose = Total Tablets taken*60.
Concomitant Medications

 The following information will be added to the baseline characteristics table: 
 Concomitant Medications for UC: Participants will be categorized into one of 4 groups based on their ongoing prior concomitant medications: 
 Glucocorticoids only, Immunosuppressants only, Glucocorticoids and immunosuppressants and No glucocorticoids or immunosuppressants. Prednisone dose (or equivalent): Summary statistics will be presented. Glucocorticoids, Immunosuppressants and Prednisone will be identified by review of GSK drug terms by clinical and medical team.

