Study Duration and Dosing	
 Each participant will participate in the study for approximately 20 weeks. This includes a screening period up to 30 days, an 84-day (12 week) treatment period, and a 28-day follow-up period after the last dose. Within 30 days of the screening visit (defined as day of consent signing), eligible participants enter a 2-part treatment phase as follows with study treatment starting on study day 1: 
 Part A: Approximately 36 participants are randomly assigned to receive either GSK2982772 60 mg three times daily (TID) or placebo TID for 42 days (6 weeks) in a 2:1 ratio. Part B: All participants who complete Part A move on to receive open label treatment of GSK2982772 60 mg TID for an additional 42 days (6 weeks). Treatment duration is a total of 84 days (12 weeks) inclusive of Parts A and B. Participants are followed-up for 28 days (4 weeks) after the last dose in Part B. Prior to amendment 01 being effective in each country, participants were randomly assigned to receive either: 
 Part A: GSK2982772 60 mg two times daily (BID) or placebo BID for 42 days (6 weeks) in a 2:1 ratio. Part B: Open label treatment for all participants who have completed Part A of GSK2982772 60 mg BID for an additional 42 days (6 weeks). 																															
Time & Events	
 Refer to Appendix 2: Schedule of Activities. During the 84-day (12 week) treatment period, participants attend the clinical for visits on Days 1, 15, 29, 43, 57, 71 and 85. At specific visits, participants must not take treatment prior to their scheduled treatment. On Days 8, 22, 36, 50, 64 and 78 participants were to be contacted by telephone and asked about their general health. Participants are given a diary card at every visit and asked to record daily study 																															

Overview of Study Design and Key Features	
	medication, concomitant medication and adverse events.

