6.1.1. Study Population Summary Measure

Population analyses will be presented (summarised in tables and listed) by randomised treatment group only.

Table 2 Overview of Planned Study Population Analyses

Endpoint / Parameter / Display Type	Data Displays Generated		
	Table	Figure	Listing
Subject Disposition			
Subject Disposition for the Subject Conclusion Record	Y		
Treatment Status and Reasons for Discontinuation of Study Treatment	Y		Y
Screen Status and Reason for Screen Failure	Y		Y
Subjects by Country and Site ID	Y		
Reasons for Subject Withdrawal			Y
Subjects for Whom the Treatment Blind was Broken			Y
Planned and Actual Treatments			Y
Protocol Deviations			
Important Protocol Deviations	Y		Y
Subjects with Inclusion/Exclusion Criteria Deviations			Y

Endpoint / Parameter / Display Type	Data Displays Generated		
	Table	Figure	Listing
Populations Analysed			
Study Populations	Y		
Exclusion from Any Population	Y		Y
Demographic and Baseline Characteristics			
Demographic Characteristics	Y		Y
Age Ranges	Y		
Race and Racial Combinations	Y		Y [1]
Ulcerative Colitis Baseline Characteristics [2]	Y		Y
Prior/Current Medical Conditions and Concomitant Medications [3]			
Medical Conditions	Y		Y
Concomitant Medications [4]	Y		Y
Cardiovascular Risk Factors	Y		Y
Exposure and Treatment Compliance			
Exposure to Study Treatment	Y		Y
Study Drug Accountability			Y

NOTES:

- Y = Yes display generated.

1: Listing of race.

2: Baseline characteristics including: Baseline Mucosal Appearance at Endoscopy Mayo Subscore, Baseline Total Mayo Score, Baseline Partial Mayo Score, Baseline 3-domain Mayo Score, Baseline UCEIS Total Score, Baseline Modified Riley Scale, Baseline FCP, Baseline FCP category, Baseline concomitant medications for UC (Glucocorticoids only, Immunosuppressants only, Glucocorticoids and immunosuppressants, No glucocorticoids or immunosuppressants), Baseline Prednisone dose, Family History of Premature Coronary Artery Disease and History of Tobacco Use.

3: Separate summaries for Current and Past Medical Conditions/Cardiovascular Risk Factors/Concomitant Medications.

4: The ingredients of concomitant medications will be reviewed by the clinical and medical team to determine baseline use of Glucocorticoids, Immunosuppressants and Prednisone.

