1.11.	Safety	DM1	Summary of Ulcerative Colitis Baseline Characteristics by Randomised Treatment	
To include: Baseline Mucosal Appearance at Endoscopy Mayo Subscore, Baseline Total Mayo Score, Baseline Partial Mayo Score Baseline 3-domain Mayo Score, Baseline UCEIS Total Score, Baseline Modified Riley Scale Score, Baseline FCP, Baseline FCP category, Baseline Concomitant Medications for UC (Glucocorticoids only, Immunosuppressants only, Glucocorticoids and Immunosuppressants, No Glucocorticoids or Immunosuppressants, Baseline Prednisone dose, Family History of Premature Coronary Artery Disease and History of Tobacco Use.
 
Include the footnote: Note: Glucocorticoids and Immunosuppressants were identified by review of all ingredients by clinical and medical team.
	IA SAC[1], SAC [1]
Prior/Current Medical Conditions and Concomitant Medications					
1.12.	Safety	MH4	Summary of Current/Past Medical Conditions by Randomised Treatment	
ICH E3 Separate summaries for Current & Past conditions, if collected.
	IA SAC [1], SAC [1]

Study Population Tables					
No.	Population	IDSL / Example Shell	Title	Programming Notes	Deliverable [Priority]
1.13.	Safety	MH1	Summary of Current/Past Cardiovascular Risk Factors by Randomised Treatment	ICH E3 Separate summaries for Current & Past, if collected	IA SAC [1], SAC [1]
1.14.	Safety	CM1	Summary of Prior Medications by Randomised Treatment	ICH E3	IA SAC [1], SAC [1]
1.15.	Safety	CM1	Summary of Concomitant Medications by Randomised Treatment	ICH E3	IA SAC [1], SAC [1]
Exposure and Treatment Compliance					
1.16.	Safety	EX1 / EX5	Summary of Exposure to Study Treatment by Randomised Treatment	ICH E3	IA SAC [1], SAC [1]

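### Exposure and cumulative dose run over Parts A and B together and are summarised by randomised arm only, so a placebo-arm completer is credited with 84 days and double the dose from the drug tablets taken

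*SAP*

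**What the plan says.** Section 2.3 sets the design. "Approximately 36 participants are randomly assigned to receive either" drug or placebo, the latter being "or placebo TID for 42 days (6 weeks) in a 2:1 ratio". Everyone who completes Part A then takes open-label GSK2982772 for 42 more days: "Treatment duration is a total of 84 days (12 weeks) inclusive of Parts A and B".

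Section 12.6.2 describes its measure as days of exposure to study drug and defines it as "Duration of Exposure in Days = Treatment Stop Date – (Treatment Start Date) + 1". Section 12.4.1 uses the study treatment stop date to close Part B, so for a completer the span covers both parts. Tablets taken are all those dispensed less all those returned. Then "Cumulative Dose = Total Tablets taken*60", with no condition on whether a tablet was active or placebo.

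On display, section 6.1.1 states: "Population analyses will be presented (summarised in tables and listed) by randomised treatment group only". The one exposure table, Table 1.16 in section 12.10.4, is titled "Summary of Exposure to Study Treatment by Randomised Treatment". Listings 14 (exposure) and 15 (drug accountability) are also by randomised treatment.

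The safety outcomes are handled differently. Sections 7.1.1, 7.2.1 and 7.3.1 present adverse events, laboratory data, ECGs and vital signs by randomised treatment and also by period treatment, meaning the treatment actually received.

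**The concern.** Safety and tolerability of GSK2982772 is the primary objective, and section 2.4 plans no formal hypothesis test for it. The conclusion will be descriptive, so the reader needs to know how much exposure to the drug stands behind it.

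For the placebo arm the planned derivations do not give that. Days on placebo and days on drug are merged into one figure described as exposure to study drug, and placebo tablets are converted into a drug dose. A placebo participant who withdraws during Part A has taken no GSK2982772 at all, yet still gets a positive cumulative dose.

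The adverse event tables by period treatment can place up to 24 + 12 = 36 participants under GSK2982772. The only exposure table places 24 there, so those safety tables have no exposure summary on the same basis.

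**Working it through.** The SAP gives no exposure total to reproduce. Its one relevant sum agrees with its parts: 42 + 42 = 84 days.

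**Inputs**
- 36 participants at 2:1, so 24 drug and 12 placebo (section 2.3).
- Part A 42 days; Part B 42 days, all on GSK2982772 (section 2.3).
- Six tablets a day for TID participants (section 12.6.2, compliance).
- Multiplier of 60 per tablet (section 12.6.2, cumulative dose).
- Withdrawal is not given. Assumed 0%, with a range to 30%.

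**One completer on TID, by the SAP formulas**

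| | Drug arm | Placebo arm |
|---|---|---|
| Duration as derived | 84 | 84 |
| Days on GSK2982772 | 84 | 42 |
| Tablets counted | 84 × 6 = 504 | 84 × 6 = 504 |
| GSK2982772 tablets | 504 | 42 × 6 = 252 |
| Cumulative dose as derived | 504 × 60 = 30,240 | 504 × 60 = 30,240 |
| Same formula, GSK2982772 tablets only | 30,240 | 252 × 60 = 15,120 |

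With any per-tablet figure d, the placebo completer gets 504d against 252d for the GSK2982772 tablets. The ratio is 2 and does not depend on d.

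**Aggregate days, for illustration**
- Drug days in the drug arm: 24 × 84 = 2,016.
- Drug days in the placebo arm: 12 × 42 = 504.
- All drug days: 2,016 + 504 = 2,520. Share in the placebo arm: 504 / 2,520 = 20.0%.
- Placebo-arm days as derived: 12 × 84 = 1,008, of which 12 × 42 = 504 are placebo days.

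**Sensitivity to withdrawal.** Let a fraction w leave at the end of Part A.
- Both arms: 12(1−w)42 / [24×42 + 24(1−w)42 + 12(1−w)42]
- Placebo arm only: 12(1−w)42 / [24×84 + 12(1−w)42]
- Drug arm only: 12×42 / [24×42 + 24(1−w)42 + 12×42]

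| w | Both arms | Placebo only | Drug only |
|---|---|---|---|
| 10% | 19.2% | 18.4% | 20.8% |
| 20% | 18.2% | 16.7% | 21.7% |
| 30% | 17.1% | 14.9% | 22.7% |

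The share therefore runs from about 15% to 23%. The one BID participant (section 5.1, arm not stated) leaves days unchanged.

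**A separate conflict in section 12.6.2.** The compliance rule counts two tablets per intake, six a day for TID. The dose rule multiplies each tablet by 60, so a TID day gives 6 × 60 = 360. The stated regimen of 60 mg three times daily gives 3 × 60 = 180 mg. Over 84 days that is 30,240 against 84 × 180 = 15,120. For a placebo completer it is 30,240 against 42 × 180 = 7,560, a factor of 4: one factor of 2 from counting placebo tablets, one from this conflict. The document does not show which entry is at fault.

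**The case against.** Several points on the other side stand.

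- **A reader might infer that Table 1.16 will print 2,016 and 1,008 days.** The SAP does not plan that. Section 12.5.2 summarises continuous data by mean, median, SD, SE, minimum and maximum. With full completion the table would show a mean of 84 days in each arm, which is correct for time on any study treatment, the term in the table's title. It is not correct for time on GSK2982772.
- **A reader might infer that the plan understates exposure to drug throughout.** That holds for days under the GSK2982772 label, not for dose. With the multiplier as written, 24 drug-arm completers total 24 × 30,240 = 725,760. The stated regimen gives 24 × 15,120 + 12 × 7,560 = 453,600 mg for both arms together.
- **A reader might fault compliance for being pooled over both parts.** Placebo tablets belong in compliance, so pooling is not an error. At most it can hide a difference between the parts.
- **A reader might infer that no output at all will show exposure to drug.** The shells for Listings 5, 14 and 15 are not shown, and records by period within them cannot be ruled out. Only the absence of a planned summary table is established.
- **No exposure-adjusted event rate is planned.** No safety denominator uses this duration, and adverse events are already shown for Part A alone and by period treatment.

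These narrow the point but do not remove it. A reader could not recover drug exposure by subtracting 42 days: withdrawals differ, the Day 43 visit has a window of ±3 days, and tablets and dose do not follow from dates.

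**Conclusion.** The point holds for duration described as exposure to study drug and for cumulative dose. Applied as written, section 12.6.2 gives a placebo-arm completer 84 days where 42 were on GSK2982772, and a dose twice that from the GSK2982772 tablets taken. The factor of 2 assumes completion of both parts and full intake; it does not depend on the per-tablet figure. No planned summary table gives exposure on the period-treatment basis used for the safety outcomes.

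The aggregate of 20% of drug days in the placebo arm assumes 24:12 and full completion; the range of 15 to 23% assumes up to 30% withdrawal at the end of Part A. Both indicate scale only.

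This is a descriptive error that should be corrected before reporting. It biases no treatment comparison and no planned event rate. The cumulative dose is nonetheless a wrong number and not merely a matter of presentation.

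**What to change.** 1. In section 12.6.2, derive duration, tablets taken and cumulative dose separately by part. Part A runs from first dose to the day before the first open-label dose, or to treatment stop if earlier. Part B runs from the first open-label dose to treatment stop. This gives 42 + 42 = 84. Ending Part A on Day 43 itself would give 43 + 42 = 85, because schedule footnotes 10 and 11 move participants to Part B at the Day 43 visit and have that morning's dose given on site.
2. Count only GSK2982772 tablets in cumulative dose.
3. Amend section 6.1.1 and add a version of Table 1.16 by period treatment, using the descriptors already in section 5.1. Keep the randomised-arm version.
4. Reconcile the two-tablet intake with the 60-per-tablet multiplier in section 12.6.2.

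Compliance by part is optional.

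The cost is SAP wording and one added table. Duration by part should need no new data. Tablet counts by part depend on returns having been recorded at Day 43: the schedule shows medication dispensed at that visit but has no row for returns. If returns were not recorded then, report duration by period and do not report a cumulative dose that includes placebo tablets.

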2.2. Study Objective(s) and Endpoint(s)

Objectives	Endpoints
Primary Objectives	Primary Endpoints

 To investigate the safety and tolerability of 60 mg three times daily doses of GSK2982772 in subjects with moderate to severe ulcerative colitis. 	
 Adverse events. Clinical laboratory values (clinical chemistry, haematology and urinalysis). Vital sign measurements (blood pressure, heart rate, respiratory rate, and body temperature). 12-Lead ECG monitoring.
Secondary Objectives	Secondary Endpoints

 To investigate the preliminary efficacy of 60 mg three times daily doses of GSK2982772 in achieving mucosal healing after 6 and 12 weeks of treatment in subjects with active ulcerative colitis. 	
 The proportion of subjects who achieve an absolute Mayo endoscopy subscore of 0 or 1 at Days 43 (Week 6) and 85 (Week 12). Change from baseline in mucosal appearance determined by Ulcerative Colitis Endoscopic Index of

Objectives	Endpoints

 To investigate the effect of 60 mg three times daily doses of GSK2982772 on biomarkers of disease activity in subjects with active ulcerative colitis. 	Severity (UCEIS). 
 Change from baseline in markers which may include, but are not limited to, mean CRP and faecal calprotectin (FCP).

 To investigate the effect of 60 mg three times daily doses of GSK2982772 on histologic disease activity in subjects with active ulcerative colitis. 	
 Change from baseline in histologic severity, including but not limited to Modified Riley Score and Geboes Index.

 To investigate the effect of 60 mg three times daily doses of GSK2982772 in achieving clinical response and remission after 6 and 12 weeks of treatment in subjects with active ulcerative colitis. 	
 The proportion of subjects who achieve clinical response defined as reduction by ≥ 3 points or $\geq 30\%$ improvement from baseline complete Mayo score, along with a decrease in the rectal bleeding score of ≥ 1 point, at Days 43 (Week 6) and 85 (Week 12). The proportion of subjects who achieve clinical remission defined as a complete Mayo score of 2 points or lower, with no individual subscore exceeding 1 point, at Days 43 (Week 6) and 85 (Week 12).

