5. CONSIDERATIONS FOR DATA ANALYSES AND DATA HANDLING CONVENTIONS

5.1. Study Treatment & Sub-group Display Descriptors

One subject was randomised to a BID regimen before the protocol was amended. Per instructions in the protocol, data will be summarised in tables and figures by treatment (GSK2982772 60mg or Placebo) irrespective of dosing regimen received (BID or TID). Data will be listed per treatment and dosing regimen received (BID or TID). Some key safety endpoints will be summarised by both randomised treatment and period treatment, details are provided in [Appendix 9](#).

Should a participant receive the wrong medication at any point during the study in error, that participant will be treated as having received GSK2982772 60mg TID for the duration of the study.

Randomised Treatment Group Descriptions					
RandAll NG		Data Displays for Reporting			
Code	Description	Description in tables/non-PK figures	Order in TF	Description in Listings/PK figures	Order in Listing
A	GSK2982772 60mg BID (Double-blind)	GSK2982772 60mg	2	GSK2982772 60mg BID	3
C	GSK2982772 60mg TID (Double-blind)	GSK2982772 60mg	2	GSK2982772 60mg TID	4
P	Placebo BID (Double-blind)	Placebo	1	Placebo BID	1
Q	Placebo TID (Double-blind)	Placebo	1	Placebo TID	2

Period Treatment Group Descriptions					
RandAll NG		Data Displays for Reporting			
Code	Description	Description in tables	Order in TF	Description in Listings	Order in Listing
A	GSK2982772 60mg BID (Double-blind)	GSK2982772 60mg	2	GSK2982772 60mg DB BID	3
B	GSK2982772 60mg BID (Open-label)	GSK2982772 60mg	2	GSK2982772 60mg OL BID	5
C	GSK2982772 60mg TID (Double-blind)	GSK2982772 60mg	2	GSK2982772 60mg DB TID	4
D	GSK2982772 60mg TID (Open-label)	GSK2982772 60mg	2	GSK2982772 60mg OL TID	6
P	Placebo BID (Double-blind)	Placebo	1	Placebo DB BID	1
Q	Placebo TID (Double-blind)	Placebo	1	Placebo DB TID	2

Treatment comparisons will be displayed as follows using the descriptors as specified:

- GSK2982772 60mg vs Placebo.

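### Tablet compliance and cumulative dose in SAP 12.6.2 cannot both be right for a 60 mg dose: one counts two tablets per administration, the other credits 60 to every tablet

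*SAP*

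**What the plan says.** Three parts of the SAP bear on this.

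- **Regimen.** Section 2.2 sets the primary objective as the "safety and tolerability of 60 mg three times daily doses of GSK2982772". Section 2.3 carries the same dose into the open-label part ("All participants who complete Part A move on to receive open label treatment of GSK2982772 60 mg TID"). Before amendment 01 the frequency differed but the dose per administration did not: "GSK2982772 60 mg two times daily (BID) or placebo BID for 42 days (6 weeks) in a 2:1 ratio". Section 5.1 records that "One subject was randomised to a BID regimen before the protocol was amended".
- **Compliance (section 12.6.2, Treatment Compliance).** The expected number of tablets "will depend on whether a participant was taking investigational product (two tablets) twice a day or three times a day". The rule is then put in figures: "Total Tablets expected to be taken is duration of exposure*4 (see derivation below) for BID participants and *6 for TID participants". The numerator is "Total tablets taken = (Total number of Tablets Dispensed-Total Tablets Returned").
- **Cumulative dose (section 12.6.2, Extent of Exposure).** The whole definition is "Cumulative Dose = Total Tablets taken*60". The multiplier has no unit.

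The SAP does not state a tablet strength anywhere.

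**The concern.** The two derivations share one input, the number of tablets taken, but imply different things about a tablet. The compliance rule spreads an administration over two tablets. The cumulative-dose rule gives each tablet the figure that the rest of the SAP uses for a whole administration. Either rule alone could fit a 60 mg administration; the pair cannot.

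The trial's primary objective is safety and tolerability without formal hypothesis testing (section 2.4), so descriptive summaries carry it, and exposure is the context in which adverse events are read. A programmer following the text would produce an exposure measure that is wrong by a factor of two, and independent programming from the same specification would reproduce the error rather than catch it.

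**Working it through.** **Inputs**

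| Input | Value | Source |
|---|---|---|
| Dose per administration | 60 mg | SAP 2.2, 2.3; 12.2.1 footnote 11 |
| Administrations per day | 3 (TID), 2 (BID) | SAP 2.3 |
| Expected tablets per day | 6 (TID), 4 (BID) | SAP 12.6.2, compliance |
| Amount credited per tablet | 60, no unit | SAP 12.6.2, cumulative dose |
| Treatment duration | 84 days (42 in Part A, 42 in Part B) | SAP 2.3 |

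**Step 1: consistency.** Let *n* be tablets per administration and *s* the mg per tablet. The regimen requires *n* × *s* = 60. The compliance rule sets *n* = 6/3 = 4/2 = 2. The cumulative-dose rule sets *s* = 60, reading the multiplier as mg. Then *n* × *s* = 2 × 60 = 120, not 60. The three statements have no common solution.

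**Step 2: case (a), two tablets make up one 60 mg administration.** Then *s* = 60/2 = 30 mg, and the cumulative-dose formula overstates. For a participant randomised to active drug:

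| Scenario | Tablets taken | SAP formula (tablets × 60) | Dose by regimen (tablets × 30), mg | Ratio |
|---|---|---|---|---|
| TID, 84 days, full intake | 84 × 6 = 504 | 30,240 | 15,120 | 2.0 |
| TID, 42 days, full intake | 42 × 6 = 252 | 15,120 | 7,560 | 2.0 |
| TID, 84 days, 75% intake | 0.75 × 504 = 378 | 22,680 | 11,340 | 2.0 |
| BID, 84 days, full intake | 84 × 4 = 336 | 20,160 | 10,080 | 2.0 |

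The full-intake rows agree with days × administrations × 60 mg: for example, 84 × 3 × 60 = 15,120.

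**Step 3: case (b), one 60 mg tablet per administration.** Cumulative dose is then right, but the compliance denominator is twice too large:

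| Scenario (84 days) | Tablets taken | Tablets expected by the SAP | Compliance shown | True compliance |
|---|---|---|---|---|
| TID, full intake | 84 × 3 = 252 | 504 | 50% | 100% |
| BID, full intake | 84 × 2 = 168 | 336 | 50% | 100% |
| TID, 75% intake | 0.75 × 252 = 189 | 504 | 37.5% | 75% |

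In both cases the factor is exactly two, whatever the duration or intake. With any other tablet strength, both formulas would be wrong.

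**The case against.** The contradiction itself is hard to dispute; the fair objections concern its weight.

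- **It may not reach any output.** The displays listed in section 6.1.1 (Table 2) are exposure to study treatment and drug accountability; no display title names cumulative dose or percentage compliance. The shells for Table 1.16 and Listings 14 and 15 are not shown. This stands as a limit on what can be demonstrated. However, section 6.1 plans analyses of exposure and treatment compliance, and section 12.6.2 specifies both variables for programming.
- **Nothing downstream depends on it.** This is correct. The per-protocol exclusions in section 12.1.1 contain no compliance criterion, and the PK/PD displays use concentrations.
- **Case (b) is less likely.** The compliance text gives two tablets consistently: in words and through both daily factors. Case (b) needs all of these to be wrong, whereas case (a) needs only one multiplier to be wrong. This is a reasonable reading of the balance, but without a tablet strength the SAP does not settle it.
- **Tablet strength belongs in the protocol.** It may well be there. That would show which formula to change; it would not make the two agree.
- **One of the two tablets might be inactive.** The SAP does not say so, and it would not help, because the formula multiplies every tablet taken.
- **The placebo arm is different.** Under 2:1 allocation, one third of participants are planned to take placebo in Part A. For them the size of the error depends on whether cumulative dose means study treatment or GSK2982772 alone. This is a separate ambiguity and adds no weight to the factor of two.

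**Conclusion.** The concern holds. The compliance rule, the cumulative-dose rule and the 60 mg administration cannot all be true, so at least one exposure measure is wrong if the plan is followed as written. In the two simplest cases the error is exactly twofold: cumulative dose doubled if tablets are 30 mg, or displayed compliance halved if one 60 mg tablet is taken each time. Both cases are assumptions because the SAP gives no tablet strength. The doubling is worked out for participants randomised to active drug and reads the multiplier as mg.

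The reach is narrow. Only descriptive outputs are affected (Table 1.16 and Listings 14 and 15, scheduled for both interim and final reporting), and only to the extent that they show these variables. It should be corrected because the inconsistency is certain and the correction is almost free, but it threatens no inferential result.

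**What to change.** Reconcile the Treatment Compliance and Extent of Exposure entries in section 12.6.2:

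1. State the mg per tablet, by citing the protocol or study-drug documentation if it is given there.
2. Make the daily tablet factors and the cumulative-dose multiplier agree with that strength and with the dose per administration in sections 2.2 and 2.3.
3. Give cumulative dose a unit.
4. As a separate clarification, say whether cumulative dose covers all study treatment, including placebo tablets, or GSK2982772 only.

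The cost is one sentence, one corrected formula and a small change to the exposure or compliance program. No new data are needed.
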